### 5.2.3 Study Treatment Phase Criteria

#### 5.2.3.1 Treatment Phase - INCLUSION Criteria:

After the washout phase, the following are requirements a subject must meet in order to be considered for enrollment into the treatment phase of the study:

- 1) After the six-week washout phase, the subject continues to meet all screening phase inclusion/exclusion criteria
- 2) After the six-week washout phase, subject's Baseline (Visit 2) IOP, measured between 8:00 and 10:00 AM, is  $\geq 23.0$  and  $\leq 34.0$  mmHg in at least one eye

- 3) Subject's Baseline (Visit 2, morning average) IOP is  $\geq$  5 mmHg from the subject's SCREENING (pre-washout) IOP in at least one eye whose Baseline IOP is between  $\geq$  23 and  $\leq$  34 mmHg.
- 4) Investigator is able to dilate the lower puncta of each eye to 1.0 mm, and insert a study plug into each puncta.

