#### 5.4.1 Reasons for Termination, Discontinuation or Disqualified

**At a study subject's last visit (scheduled or unscheduled), a study subject will have his/her study punctal plugs removed** and a study exit case report form (CRF) must be completed, whether or not the study subject completed the final study visit (Visit 7, day 90 ± 7 post-insertion). The reason for any early exiting from the study will be indicated on the study exit form and all efforts will be made to complete and report the observations as thoroughly as possible. The primary reason for a study subject early exiting the study should be selected from the following standard categories (see Sections [5.4.2](#) below).

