## 7.10 Rescue Medication(s)

### 7.10.1 Administration of a Rescue Medications

A subject with an elevated IOP (>34 mmHg) or undue medical risk in either eye should be prescribed his/her glaucoma regimen they were using prior to entering the study. The use of a rescue medication will be considered prohibited medication and will be considered a protocol deviation and the study subject will be terminated from the study. Reason for termination on the exit form should be listed as "due to lack of efficacy".

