## 10 STATISTICAL CONSIDERATIONS

### 10.1 Statistical and Analytical Plans

The primary analysis population will be an ITT (Intent-to-Treat) analysis for all study subjects who had the lower puncta of each eye inserted with a study punctal plug and had no major protocol violations. Individual study subjects or individual visits may be excluded if a major protocol violation occurs (such as violation of inclusion/exclusion criteria or non-compliance with protocol requirements that can potentially have significant impact on study outcomes).

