### 10.4 Description of Statistical Methods

#### 10.4.1 General Approach

Descriptive statistics (i.e., mean, standard deviation, etc.) will be provided for all continuous variables and frequency distributions will be generated for all categorical variables collected in this study. Analyses of the intent-to-treat (ITT) data set, will include all data from all subjects with a recorded screening visit IOP OU. Per protocol (PP) analyses dataset, will exclude data from subjects or visits with significant protocol deviations (e.g., IOPs obtained before 8:00 AM and after 10:00 AM will be excluded).

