#### 10.4.2 Analysis of Primary Study Variable

The primary study outcome variable will be the change in IOP at Visits 4, 5, 6 and 7 (Days 7, 28, 60 and 90 days post-insertion) compared with the Baseline IOP (Visit 2, Day 0), obtained between 8:00 and 10:00 AM. The unit of analysis will be the study eye at visit 2 with the highest post-washout IOP. Observed IOP and percent change from baseline in IOP will also be analyzed.

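### Section 10.1 permits a rescued plug failure to be dropped from the primary population after its IOP is known, and the later visit means describe only subjects who did not fail

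*Combined protocol and SAP*

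**What the plan says.** Section 7.10.1 makes rescue an instruction to the investigator: if either eye exceeds 34 mmHg or is at undue medical risk, the earlier regimen should be prescribed again. The same section then says: "The use of a rescue medication will be considered prohibited medication and will be considered a protocol deviation". The subject is terminated and the exit form gives lack of efficacy as the reason.

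The analysis population is described twice. Section 10.1 calls the primary population intent-to-treat but limits it to subjects "who had the lower puncta of each eye inserted with a study punctal plug and had no major protocol violations". It continues: "Individual study subjects or individual visits may be excluded if a major protocol violation occurs". Its examples of a major violation are eligibility breaches and non-compliance that could materially affect outcomes. Section 10.4.1 describes an intent-to-treat set that "will include all data from all subjects with a recorded screening visit IOP OU", and a separate per-protocol set without significant deviations.

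For the primary variable, Section 10.4.2 states: "The unit of analysis will be the study eye at visit 2 with the highest post-washout IOP". It gives no rule for IOP after rescue or plug removal, and none for missing visits.

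Some handling of failures does exist:
- Section 5.4.1 on exit reasons: "The primary reason for a study subject early exiting the study should be selected from the following standard categories".
- Section 10.4.1 promises that "frequency distributions will be generated for all categorical variables collected in this study", so exits for lack of efficacy should be counted.
- Section 8.1 lists rescue use as a safety variable.
- Section 5.4.3.1 treats terminated subjects as having completed the study and does not replace them.

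**The concern.** One event is recorded both as a treatment failure and as a protocol deviation. Restarted pressure-lowering drops can be argued to fit the Section 10.1 description of a violation that matters, because the outcome is IOP. The subjects who say most about plug failure are thus the ones whose place in the primary population is left to judgement.

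That judgement would be made with the data in view. The study is open-label, Section 10.4.7 has data analysed on an ongoing basis, and Section 10.6 lists no measures against bias. Section 8.8 lets the study stop early if efficacy looks sufficient for phase III. With no control arm, the mean changes at Days 28, 60 and 90 are the evidence for a sustained effect, so it matters which subjects stand behind each of them.

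**Working it through.** The documents state no rescue rate, effect size, SD or power for this study, so there is no planned figure to reproduce. The check is a reading of the rules followed by an illustration.

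**Rules side by side**

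| Question | Text | Consequence |
|---|---|---|
| Is rescue a major violation? | 7.10.1 says deviation; 10.1 says major violation and gives only examples | Open to judgement |
| Must a violator be dropped? | 10.1 limits the population to subjects without major violations, then says subjects or visits may be excluded | Permitted, not required, for a rescued subject |
| Does 10.4.1 settle it? | All data from subjects with a screening IOP | Conflicts with 10.1, and includes subjects never fitted with plugs |
| Is there on-plug IOP after rescue? | 7.10.1 terminates; 5.4.3.1 removes the plugs | No, whatever 10.1 says |
| Can on-drops IOP enter? | 7.4.3.6(h) reads IOP before plug removal; 7.6 applies Visit 7 procedures at early exit; 5.4 follows terminated subjects to Day 90 or until the condition resolves or stabilises | Only through an exit exam after drops restart, or a follow-up reading mapped to a visit |
| Is a rescued subject replaced? | 7.10.1 with 5.4.3.1: terminated, not replaced. 5.4.2.1(f) with 5.4.3.2: users of prohibited medication discontinued and replaced | Arguable, although 7.10.1 is the more specific rule |

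**Illustration**

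Inputs: N = 30 (the Section 5.1 maximum). The 29 non-rescued subjects change by m = -7 mmHg, an assumption taken from the 7 to 8 mmHg reduction with travoprost drops in Appendix I. One subject is rescued with an analysed-eye reading of 35 from a baseline of 30, so x = +5 (assumed; 35 meets the above-34 trigger).

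Mean with the subject kept = (29m + x)/30. Mean with the subject dropped = m.

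- Trigger visit, kept: (29 × (-7) + 5)/30 = -198/30 = -6.60.
- Trigger visit, dropped: -7.00. The mean looks better by 0.40 mmHg.
- Later visits, observed data: the subject has no on-plug value, so the mean is -7.00 under either population.
- Later visits, sensitivity analysis carrying +5 forward: -6.60.

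Varying the assumptions for one rescued subject, the shift from dropping is (x - m)/30:

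| m | x = +1 | x = +7 |
|---|---|---|
| -7 | 8/30 = 0.27 | 14/30 = 0.47 |
| -5 | 6/30 = 0.20 | 12/30 = 0.40 |

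**Direction.** Suppose the other eye triggers rescue while the analysed eye is at 21 from a baseline of 30 (change -9). Kept: (29 × (-7) - 9)/30 = -212/30 = -7.07. Dropped: -7.00. Dropping now makes the mean look worse by 0.07. This case is possible because 7.10.1 applies to either eye, and Section 5.2.3.1 requires the Visit 2 range of 23 to 34 "mmHg in at least one eye", not in both.

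**Chance that it arises.** At assumed rescue rates of 3%, 5% and 10%, the chance of at least one rescue in 30 is 1 - 0.97^30 = 60%, 1 - 0.95^30 = 79% and 1 - 0.90^30 = 96%. These rates are not from the documents.

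**The case against.** The strongest reply is that the protocol itself directs rescue, so rescue is not plainly non-compliance, and that 7.10.1 never calls it major. This stands in part. A reader might infer that Section 10.1 requires plug failures to be removed; the text only permits it.

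A second reply is that the later-visit gap comes from termination and plug removal, not from the population definition. This also stands. A reader might infer that repairing Section 10.1 would correct the Day 60 and Day 90 means. It would not: a subject rescued at Day 28 has no on-plug value afterwards under any definition. What Section 10.1 can remove is the trigger reading and the earlier on-plug visits.

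A third reading is that IOP on restarted drops will routinely be counted as plug IOP. The documents do not support that. IOP is read before plug removal, and the primary variable is confined to Visits 4 to 7. The remaining routes are narrow, though nothing closes them.

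Nor does the bias always favour the plug, as the other-eye case shows. How often that case can occur depends on whether study eye in Section 10.4.2 means a qualifying eye. If it does not, an eye above 34 at Visit 2 could itself be the analysed eye.

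Finally, this is a pilot with no formal sample size, and failures will appear in the exit-reason and safety tables. That limits the harm, but those tables do not show which subjects stand behind each IOP mean.

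**Conclusion.** The point holds in a limited form. The plan gives two incompatible definitions of the primary set and leaves it open, once the data have been seen, whether a rescued subject's trigger reading and earlier visits count. Separately, the later means describe only subjects who did not fail, and nothing planned beside those means shows this. On-drops IOP entering the primary variable is a minor residual risk.

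The size cannot be derived from the documents and could be zero. Under the assumptions shown, with the analysed eye as the trigger, dropping one rescued subject in 30 improves the trigger-visit mean by 0.20 to 0.47 mmHg. The direction can reverse when the other eye or undue medical risk is the trigger. This is a worthwhile, inexpensive improvement and not a fault that invalidates the study.

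**What to change.** **Section 10.1.** Define one primary population: all subjects with both plugs inserted. State that rescue, or termination for lack of efficacy, is not a ground for excluding a subject or any pre-rescue visit. Align the intent-to-treat wording in Section 10.4.1 with it.

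**Section 10.4.2.** Exclude from the primary variable any IOP taken after the first rescue dose or after plug removal. Show beside each visit mean the cumulative number rescued or terminated for lack of efficacy. Add a sensitivity analysis that carries the analysed eye's last pre-rescue IOP to later visits, including an exit reading outside the visit windows. That allowance matters because the four primary windows cover only 3 + 7 + 11 + 15 = 36 of the 97 days after insertion.

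**Sections 7.10.1 and 5.4.2.1.** State that rescued subjects are terminated and not replaced under 7.10.1 and 5.4.3.1, and do not fall under 5.4.2.1(f) and 5.4.3.2.

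**Cost.** A few sentences. Medication start dates (Section 7.8.2) and plug removal dates (Section 11.1) are already recorded; only the order of IOP and first rescue dose on the same day would be new. Later-visit results may look slightly less favourable. The carried value was selected for being high and can overstate failure, so it should remain a sensitivity analysis.

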## 8 ASSESSMENT OF SAFETY

### 8.1 Safety Variables

Safety variables for this study will include any reported AE/ADE and rescue medication use. Safety variables will also include clinically significant changes in IOP, BCDVA, slit-lamp findings, ocular tearing and comfort, blood pressure, heart rate, temperature, extrusion of a Travoprost Evolute®, or technical issues with the study plug (e.g., cap of study plug tears or becomes separated during plug removal).

To optimize consistency of AE/SAE reporting across sites, the study subject will be asked a standard question to elicit any AE/SAE. At each study visit or telephone evaluation of the study subject, study personnel will ask the following question:

**"Have you had any problems since your last visit?"**

## **8.2 Definitions**

### **8.2.1 Adverse Event**

Adverse Event (AE): any unanticipated sign (including a clinically significant abnormal laboratory finding), symptom, or disease temporally associated with the administration of a medicinal product, whether or not considered related to the investigational product or device.

Medical conditions or diseases present before a subject starts study treatment are only considered AEs if they worsen after the subject starts study treatment.

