### **8.2.2 Serious Adverse Event**

Serious Adverse Event (SAE): defined as any AE that (at any dose):

- Results in death
- Is life-threatening. NOTE: The term "life-threatening" refers to an event in which the subject was at risk of death at the time of the event; it does not refer to an event which hypothetically might have caused death if it were more intense
- Requires inpatient hospitalization or prolongs existing hospitalization
- Results in persistent or significant disability/incapacity
- Is a congenital anomaly/birth defect
- May jeopardize the subject or may require intervention to prevent one of the outcomes listed above. Medical and scientific judgment should be exercised in deciding if these events should be considered serious. Examples of such events are intensive treatment in an emergency room or at home for allergic bronchospasm, blood dyscrasias or convulsions that do not result in hospitalization, or development of drug dependency or drug abuse.

In addition, an AE that results in overdose or produces congenital abnormality or cancer is always considered an SAE.

A subject admitted to a hospital as a result of an AE, even if released on the same day, would qualify for inpatient hospitalization. An emergency room visit that results in admission to the hospital would also qualify for inpatient hospitalization. However, emergency room visits that do not result in admission to the hospital would not qualify for inpatient hospitalization and, instead, should be evaluated for one of the other criteria for SAEs (e.g., life-threatening AE or medically significant event).

Hospitalization scheduled before a subject enrolls in the study is not the result of a treatment-emergent AE, and therefore events leading to such hospitalization will not be considered study AEs or SAEs. During the study, if a subject has elective surgery for a condition present at screening into the study, and the condition did not worsen during the study, the reason for elective surgery, and resulting hospitalization (if applicable), should not be considered or reported as an SAE. Surgery or hospitalization should always be reported as an outcome of an AE. For AEs that result in persistent or significant disability/incapacity, refers to a substantial disruption of a subject's ability to carry out normal life functions.

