#### 8.6.4 Anticipated Adverse Event

The following is a list including, but not limited to, ocular adverse events that are anticipated. Any event that is unlikely but anticipated must have an adverse event form completed and reported to Mati Therapeutics Inc. ([Section 8.7](#) for reporting details).

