##### Listing of Anticipated Ocular Adverse Events

###### DRUG:

Incidence rate 30-50%: Hyperemia (\*Hyperemia in IZBA controlled studies noted at 12%)

Incidence rate 5-10%: Decreased VA, Eye Discomfort, Foreign Body Sensation, Pain, Pruritus

Incidence rate 1-4%: Abnormal Vision, Blepharitis, Blurred Vision, Cataract, cells, Conjunctivitis, Corneal Staining, Dry Eye, eye disorder, Iris Discoloration, Keratitis, Lid Margin Crusting, Ocular Inflammation, Photophobia, Subconjunctival Hemorrhage, Tearing

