###### DEVICE:

The main risks of commercial silicone punctal plugs are ocular discomfort, epiphora (watery eyes), loss of plug (extrusion), ocular inflammation, and subconjunctival hemorrhage. Less common, but serious, side effects include but are not limited to pyogenic granuloma, damage to the muscle at the opening of the punctum, canaliculitis or migration of the plug into the canalicula (requiring irrigation or surgery)

**NOTE:** Patient treated with an ophthalmic solution of travoprost should be informed of the potential for increased brown pigmentation of the iris, periorbital and/or eyelid tissue, and increase growth of eyelashes in the treated eye

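### Section 8.2.1 limits adverse events to unanticipated ones, which contradicts 8.6.4, 8.7.2 and Appendix H; a smaller mismatch concerns adverse events before Visit 2

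*Combined protocol and SAP*

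**What the plan says.** **Definition.** Section 8.2.1 defines an AE as "any unanticipated sign (including a clinically significant abnormal laboratory finding), symptom, or disease temporally associated with the administration of a medicinal product", whether or not it is considered related to the product. It adds: "Medical conditions or diseases present before a subject starts study treatment are only considered AEs if they worsen after the subject starts study treatment". Section 8.2.2 builds on this: a serious AE is "defined as any AE that (at any dose") has one of the listed outcomes. No other definition of an AE is given.

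**Anticipated events.** Section 8.6.4 contains a "Listing of Anticipated Ocular Adverse Events". For the drug it includes "Incidence rate 5-10%: Decreased VA, Eye Discomfort, Foreign Body Sensation, Pain, Pruritus" and, in the 1-4% group, "Ocular Inflammation, Photophobia, Subconjunctival Hemorrhage, Tearing". For the device it includes "migration of the plug into the canalicula (requiring irrigation or surgery"). Its form rule reads: "Any event that is unlikely but anticipated must have an adverse event form completed". Appendix H says that plug intrusion at removal, or migration that needs massage, irrigation or punctoplasty, is to be recorded as an AE. Section 8.7.2 calls for rapid reporting of an AE that is severe, serious or unexpected.

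**Population and window.** The Synopsis, 4.2.3 and 10.4.4 place everyone who enters or qualifies for washout in the safety analysis, and the Synopsis and 4.2.3 add a separate summary of plug-inserted subjects. Section 8.7 requires AE documentation from Visit 2, and both copies of the Schedule of Assessments start AE recording there.

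**The concern.** The word *unanticipated* turns a definition that should take in every untoward event into one that takes in only surprises. Travoprost and punctal plugs both have well-described local effects, and 8.6.4 sets them out. If those effects are not AEs by definition, the AE table omits the tolerability profile that a pilot study of a new delivery system is meant to describe. Safety is in the study title, and 10.4.4 plans to report the incidence and severity of AEs. With up to 8 sites and up to 30 subjects, a difference in how a few sites read one word could change that table.

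The second question is whether AEs are collected over the same period and in the same people as the stated safety analysis, given that washout entrants are included but documentation is required only from Visit 2.

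**Working it through.** There is no stated figure to reproduce. The check is a comparison of sections.

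1. *Does the limit reach serious AEs?* By wording, yes: 8.2.2 defines a serious AE as a subset of AEs.

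2. *Could unanticipated simply mean untoward?* Not easily, because the protocol gives the opposite word its own section. Section 8.6.4 is about anticipated adverse events, names them and gives rates. Section 8.7.3, headed as unanticipated problems, describes events not previously expected, so the protocol uses the two words in the same sense.

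3. *Where is the contradiction direct?*
   - 8.2.1 against 8.6.4: an anticipated event cannot be an AE under the first, but is called one and can need an AE form under the second.
   - 8.2.1 against Appendix H: plug migration is on the anticipated list, yet is to be recorded as an AE.
   - 8.2.1 against 8.7.2: unexpected is one of three alternatives there, so an AE can qualify by being severe or serious without being unexpected.

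4. *Do other sections repair it?* Section 8.7 asks for all AEs to be reported, but uses the defined term. The form rule in 8.6.4 speaks of events that are unlikely but anticipated, which does not clearly reach the common ones.

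5. *Which data are exposed?* Visual acuity, slit-lamp findings (including the conjunctiva), IOP and vital signs are measured at every visit, so signs found there enter the safety data whatever 8.2.1 says. Discomfort, foreign body sensation, pain, pruritus and tearing have no scheduled assessment in either copy of the schedule, although tearing and comfort are safety variables in 4.2.3, 8.1 and 10.4.4. They depend on the open question asked at each visit and then on whether the site counts the answer as an AE.

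6. *Scale only.* Assume that the eye-drop rates in 8.6.4 apply to the plug and that 30 subjects are treated. Expected number affected = 30 × rate:
   - discomfort, foreign body sensation, pain, pruritus, each at 5-10%: 30 × 0.05 = 1.5 to 30 × 0.10 = 3 subjects;
   - tearing at 1-4%: 30 × 0.01 = 0.3 to 30 × 0.04 = 1.2 subjects.

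   These are subjects in whom the definition would come into play, not events lost.

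7. *Window.* AE recording is scheduled at six of the seven visits (Visits 2 to 7), and no visit is scheduled in the six weeks between Visits 1 and 2. Several routes reach into washout:
   - 7.5 records AEs at unscheduled washout visits;
   - the question and item h at Visit 2 look back to Visit 1;
   - 8.7.2 covers severe, serious or unexpected AEs during the study;
   - an exit form is completed whenever a study subject leaves.

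   For early exits, 7.6 requires the Visit 7 procedures, which include AE recording, of any study subject. The definitions list counts anyone who has signed consent as a study subject. The notes under Visits 3 to 6 limit these procedures to exits after Visit 2, and 7.6 itself dates the exit by plug removal. The two do not agree for someone who leaves during washout.

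**The case against.** The strongest reply is that this is one badly chosen word. Sections 2.3.1 and 7.7 call known effects AEs, the visit question is unrestricted, and Appendix H gives a specific instruction on migration. A sensible site would record expected effects. The first part stands: the wider meaning is probably intended. But intent does not help a site or monitor who checks an entry against the written definition, and the form rule in 8.6.4 leaves the common symptoms unclear.

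A reader might also infer that serious AEs would go unrecorded. The documents do not support that. The anticipated serious device effects are described in 8.6.4 as less common, so they fit its form rule; Appendix H covers migration; and the AE record in 8.7.1 asks whether the event is serious. No anticipated serious event can be named that would clearly be missed. Nor does the sponsor's screening of serious AE reports in 8.6.3 show that some must be anticipated, since device association has to be judged in any case. Section 8.7.3 likewise carries a relatedness test and so picks out a narrower class.

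On the window, 8.7 can fairly be read as a minimum that 7.5 and Visit 2 add to. A reader might infer that washout AEs are not collected at all; the routes listed above show otherwise. Plug-inserted subjects are also summarised separately, so a treated-only denominator exists.

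**Conclusion.** The definition is wrong as written and should be corrected. The conflict of 8.2.1 with 8.6.4, Appendix H and 8.7.2 rests on the text alone. The consequence, AE incidence in 10.4.4 that is understated or uneven across sites for common expected symptoms, is conditional on at least one site applying 8.2.1 literally. Its size cannot be computed: the documents give no rate of under-recording and do not include the CRFs. The expected counts rest on borrowed eye-drop rates and show only that the question is likely to arise.

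The window point is real but minor. What remains uncovered is mainly non-serious events in subjects who leave before Visit 2 without an unscheduled visit. The IOP, acuity, slit-lamp and vital-sign variables are not affected by either point.

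**What to change.** In 8.2.1, replace *unanticipated* with *untoward, whether or not expected*. Add expectedness as a separate attribute of each AE; it is not among the items listed in 8.7.1. In 8.6.4, delete *unlikely but* from the form rule, so that every listed event gets an AE form.

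For the second point, reconcile 8.7, both copies of the schedule, 7.6, the early-exit notes under Visits 3 to 6 and the safety population in the Synopsis, 4.2.3 and 10.4.4. The documents do not choose between two ways of doing so, and either would close the gap:
- record AEs from washout entry, including at washout exit, and align with this the sentence in 8.2.1 on conditions present before treatment; or
- state that AE incidence is summarised over plug-inserted subjects only.

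The cost is a few wording changes, one further item on the AE record and slightly more AE recording at sites. No visit or examination is added for subjects who stay in the study. The first option may need an AE entry at washout exit, if the CRFs do not already provide one.
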